Study Protocol with SAP

Title:

Evaluating the Safety and Efficacy of Fractionated Carbon Dioxide Therapy in Postoperative Lower Extremity Wound Healing

NCT number:

NCT03644849

Document date:

April 7, 2021

Upload date:

November 7, 2021

Purpose: This study will evaluate the efficacy and safety of laser therapy on postoperative lower extremity wound healing over 12 weeks. We will include adult patients who have undergone Mohs Micrographic Surgery on their lower extremities. Patients with poor immune systems, current pregnancies, uncontrolled diabetes, lower extremity venous or arterial disease will not be included in this study. After surgery patients will be randomized into two groups. One group will receive a single laser treatment immediately after their surgery on their wound while the other will not. The group not receiving laser therapy will undergo a sham laser therapy treatment. Immediately after therapy and 4, 8, and 12 weeks postoperative patients will have a follow up visit. During these visits patients wound size will be recorded, whether the wound has healed, a photograph will be taken, and the wound temperature will be measured. Patient will be given a diary to record any adverse events related to the wound and will fill out a quality of life survey.

Objectives (specific aims and hypotheses): We hypothesize that the AFL carbon dioxide ablative laser is a safe and efficacious treatment for lower extremity wounds that result from skin cancer surgery. We plan to test this hypothesis in 2 specific aims:

Aim 1. We will establish the safety and tolerability of the carbon dioxide AFL for postoperative lower extremity wounds. Patients with postoperative lower extremity wounds will be randomized to sham laser versus laser therapy. At designated time points 0-12 weeks after sham or laser treatment, patients will return to clinic for assessment of safety endpoints, including the incidence of wound infection and tolerability using a patient diary and health-related quality of life measured using a standardized generic questionnaire such as EQ. A sample size of 48 is appropriate.

Aim 2. Determine the efficacy of the carbon dioxide AFL for healing postoperative lower extremity wounds. We plan to randomize n=48 patients with post-surgical lower extremity wounds to sham versus carbon dioxide fractional laser treatment. We will determine the time to complete ulcer healing over a 12 week course of follow up. Completion of these aims will likely improve care for hundreds of thousands of patients with lower extremity ulcers by extending the use of ablative fractional lasers to a new population of patients. Future studies will be needed to address the efficacy of ablative laser technology in ulcers of other etiologies, and have the potential to impact the lives of many patients.

Study Design: Our study is a prospective, double-blinded, randomized, placebo-controlled trial evaluating the efficacy of fractionated carbon dioxide therapy in postoperative lower extremity wound healing. This study, including analysis and submission for publication, will occur from September 2018 to November 2020. Eligibility criteria will include patients older than 18 years, those with a lower extremity wound as a result of Mohs Micrographic Surgery at Saint Louis University Dermatology Des Peres, and a postoperative wound greater than 5mm in diameter. Patients must be able to understand the informed consent, willing to come to the office for treatments and capable of following posttreatment instructions. Exclusion criteria will include pregnancy, immunosuppression, uncontrolled diabetes (defined as >7% A1c in the last 3 months), peripheral vascular disease, venous insufficiency, or no desire/unable to undergo laser therapy. After informed consent is obtained, a screening visit will be performed on their Mohs surgery day and patient eligibility will be determined. Then, patients will be randomized 1:1 to a treatment or control group via computer software. One arm will receive carbon dioxide AFL

immediately postoperatively on the wound base. The second arm, which will serve as control, will receive sham laser therapy. Both patients will be given identical postoperative wound care instructions, including vaseline applied to the wound, nonstick pad to overlay the wound, and paper tape to secure the dressing. Additionally, patients will be advised to avoid baths and application of any other products to their wound. Patients will be given a diary to record observations about their postoperative wound and to note any adverse events.

Blinding: There will be one unblinded member of the team in this study which will be the clinician performing laser therapy or sham therapy, who will therefore not be involved in any data collection, but will be responsible for reporting any adverse events per IRB protocols at our institution. Other members of the research team member will be blinded to patient group assignment, and these members of the research team will collect data (see below) at subsequent visit. Additionally, patients will be blinded to treatment group. This will be achieved by having patients wear safety glasses which blind them and the wound site still anesthetized from the operation. Data collection will be done by a separate research team member who is blinded to the treatment groups.

Inclusion Criteria: Eligibility criteria will include patients older than 18 years, those with a lower extremity wound as a result of Mohs Micrographic Surgery at Saint Louis University Dermatology Des Peres, and a postoperative wound greater than 5mm in diameter. Patients must be able to understand the informed consent, willing to come to the office for treatments and capable of following post-treatment instructions.

Exclusion Criteria: Exclusion criteria will include pregnancy, breast feeding, immunosuppression, uncontrolled diabetes (defined as $>7\%$ A1c in the last 3 months), peripheral vascular disease, venous insufficiency, decompensated heart failure (NYHA class IV), peripheral neuropathy involving the treatment site, active cancer at the time of study enrollment excluding curatively treated skin cancer, and any underlying or current medical condition which, in the opinion of the Investigator, would interfere with the evaluation of the subject, or no desire/unable to undergo laser therapy. Immunosuppression will be defined as patients with HIV, AIDS, who have received an organ transplant, allogeneic bone marrow transplant, or peripheral stem cell transplant, and any other patients taking chronic doses of systemic immunosuppressive medication within 6 months prior to randomization. Examples of immunosuppressive medications include Tacrolimus, Azathioprine, Prednisone, or Methotrexate.

Patient Visits and Data Collection:

Patients will be seen at 4 separate visits to monitor safety and efficacy endpoints (4, 8 and 12 weeks post-operatively). The patient's initial visit will include preoperative screening for eligibility, informed consent procedure, and recording of past medical history and physical exam. Once the patient is deemed eligible, enrolled, and signed informed consent, they will be randomized to either carbon dioxide AFL therapy or sham laser therapy. After the patient undergoes Mohs surgery with the resultant ulcer (the defect that typically forms after Mohs), the patient will undergo either carbon dioxide laser versus sham laser therapy. We will determine presence or absence of complete healing, wound temperature, a digital photograph, quality of life, and adverse events at each visit. Healing will be determined by one of the licensed research team members and will be defined by complete epithelialization in the absence of scab/eschar.

Wound temperature will be recorded by noninvasive infrared thermographic camera. A digital photograph will be taken with a camera that has an attachment ensuring the same distance and angle at every visit. Quality of life will be determined by ED-5Q questionnaire. Adverse events will be recorded by eliciting an oral history and review of the patient's diary. Adverse events will be recorded as presence of absence of specific outcomes. Outcomes that patients will be directly questioned about include: crusting (scaly or thickened scar), swelling, burning sensation, xerosis at treatment site, pruritus at treatment site, infection, bleeding, hypertrophic or keloid scarring, burns, or color changes at treatment site. These data points will be collected at every visit, and adjudicated by a member of the research team blinded to the treatment group. Placebo treatment will consist of directing the laser system at the floor instead of the patient's wound site. The patients will be wearing safety glasses and will have their wound site still anesthetized from the operation therefore unaware if they are receiving the therapy. This group will serve as the control group to the treatment arm in the study.

Statistical / Data analysis: We estimate that 48 participants will be required to show a significant difference in time to 100% epithelialization between treatment and control during the 12 week study. A power analysis conducted in R(1) using the powerSurvEpi package(2) with alpha = 0.10 and beta = 0.20 suggested 24 participants per group or 48 total were required. We will employ various statistical techniques in addressing our study aims. For our first aim, efficacy: time to epithelialization will be modeled in a Cox regression as a function of covariates and treatment status. Temperature will be similarly modeled, but for these outcomes we will examine effects across time via a linear mixed model. For our second aim, safety: we intend to model incidence of infection as well as quality of life again across time using linear mixed models but this time based on non-inferiority comparisons. To address any attrition, we will employ per-protocol analysis. In the interest of safety, we plan to perform interim analyses at one month and discontinue the study if warranted.

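### All 48 patients called required are randomised with no margin, and attrition is met only by per-protocol analysis, so the stated 80% power does not survive more than one or two losses

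*Combined protocol and SAP*

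**What the plan says.** Three statements bear on the point.

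- Statistical / Data analysis, on the requirement: the power calculation "with alpha = 0.10 and beta = 0.20 suggested 24 participants per group or 48 total were required".
- Objectives, Aim 2, on enrolment: "We plan to randomize n=48 patients with post-surgical lower extremity wounds to sham versus carbon dioxide fractional laser treatment". Aim 1 also gives 48.
- Statistical / Data analysis, on losses: "To address any attrition, we will employ per-protocol analysis".

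The document gives no expected loss rate, no inflation of the sample size, no replacement rule and no intention-to-treat analysis. It does not define the per-protocol set. The primary efficacy model is a Cox regression of time to epithelialization.

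**The concern.** The number randomised equals the number required, so there is no visible margin. The plan allows for the possibility of attrition but answers it with an analysis that ordinarily leaves out patients who do not complete as planned. Any such removal takes the analysed number below 48.

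Loss is plausible here. Patients return at 4, 8 and 12 weeks. Patient Visits and Data Collection also places randomisation before Mohs surgery, whereas the Purpose section places it after surgery. Eligibility needs a postoperative wound above 5 mm. If randomisation does come first, a patient could be randomised and then not meet the wound criterion, which is another route out of a per-protocol set.

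What is at stake is how a null result is read. It would be set against a stated 80% when the power of the analysis performed could be in the low or mid 70s. Partial follow-up that a Cox model can use would also be discarded. Removing patients after randomisation can bias the comparison too; that is a separate issue from power, but the same change reduces it.

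**Working it through.** **Inputs from the document (Statistical / Data analysis; Aim 2; Study Design).** Alpha 0.10; power 80%; 24 per group, 48 in total; 1:1 allocation; 48 randomised.

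**Not given, so assumed.** Sidedness (both run), hazard ratio, proportion healed by week 12, and loss rate (5%, 10% and 20%).

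**Step 1: the plan's own figure.** The 48 cannot be reproduced without a hazard ratio and healing proportions. It can only be back-solved. By the Schoenfeld formula with equal groups, HR = exp[2(z_alpha + z_0.80)/√events].

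- Two-sided: z_alpha + z_0.80 = 1.645 + 0.842 = 2.486 (from unrounded values). HR = 2.05 if all 48 heal and 2.76 if half do.
- One-sided: 1.282 + 0.842 = 2.123 (from unrounded values). HR = 1.85 if all heal and 2.38 if half do.

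So 48 is attainable for a range of effects, and the document does not say which was used.

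**Step 2: power after removal.** Take 48 analysed as giving exactly 80%, with events falling in proportion to patients. The hazard ratio then cancels:

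Power = Φ[(z_alpha + z_0.80)·√(1 − loss) − z_alpha]

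For example, at 10% loss, two-sided: 2.486 × √0.90 = 2.359; 2.359 − 1.645 = 0.714; Φ(0.714) = 76.2%.

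| Loss | Two-sided | One-sided |
|---|---|---|
| 5% | 78.2% | 78.5% |
| 10% | 76.2% | 76.8% |
| 20% | 71.9% | 73.2% |

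By number of patients removed, with (48 − lost)/48 in place of 1 − loss:

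| Lost | Two-sided | One-sided |
|---|---|---|
| 1 | 79.3% | 79.4% |
| 2 | 78.5% | 78.7% |
| 3 | 77.7% | 78.1% |
| 5 | 76.1% | 76.7% |
| 10 | 71.5% | 72.8% |

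**Step 3: allow for rounding.** The 24 per group may be rounded up. If so, the unrounded total could be anything just above 46, a slack of just under two patients. Replace √(1 − loss) by √[(48 − lost)/R], where R is the unrounded requirement. Two-sided:

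- R = 47: one loss leaves 80.0%.
- R = 46.1: one loss leaves 80.7%, two leave 79.9%, five leave 77.5% and ten leave 73.0%.

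Rounding can therefore absorb one loss and very nearly two. It does not absorb five or ten.

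**The case against.** **No loss rate is given.** The attrition sentence is conditional and forecasts no amount, so every percentage above rests on an assumed rate. That stands.

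**The 80% is unverified.** With the hazard ratio, healing proportions and sidedness missing, an allowance for loss inside an unstated event probability can be neither confirmed nor excluded. That stands too. The shortfall is measured against the plan's own claim that 48 gives 80%, and cancelling the hazard ratio does not remove the need for that assumption or for proportional loss of events.

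**Per-protocol is undefined.** A patient seen healed at week 4 or 8 and then lost has already supplied the event, and a Cox model can censor the others. The document does not say that such patients are deleted. This is fair, but per-protocol analysis is offered as the answer to attrition, and its ordinary meaning is removal. If censoring was intended, the plan should say so.

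**Stronger readings that the document does not support.**

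- A reader might infer that 80% is lost with the first dropout. Step 3 shows that rounding could leave 80% after one loss, and with no slack one loss costs only about 0.7 points.
- A reader might infer that the trial is below 80% even with all 48 followed to week 12. Showing that would need a hazard ratio and healing rates, which are not given; pairing an arbitrary hazard ratio with an arbitrary healing rate would prove nothing about this plan.
- A reader might see an arithmetic error in the 48. There is none: 24 + 24 = 48. What is missing is an allowance for loss.

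**Conclusion.** The concern holds in a limited form. On the ordinary reading of per-protocol analysis, the stated power is not delivered after more than one or two losses. The shortfall is about 2 points at 5% loss, 3 to 4 points at 10% and 7 to 8 points at 20%. With the maximum rounding slack, two-sided power is still only about 77.5% after five losses and 73% after ten.

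This rests on three assumptions: 48 analysed gives 80% (or slightly more, by rounding), lost patients are removed, and events fall in proportion to patients. If lost patients are instead kept and censored, those censored late cost less power and the removal figures do not apply. The effect is modest at low loss, but it is worth correcting because the change is cheap and improves the analysis as well as the stated power.

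**What to change.** In Statistical / Data analysis:

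1. Make the primary Cox analysis of time to epithelialization include every randomised patient in the assigned group, censored at the last attended visit if not healed. Keep per-protocol as a sensitivity analysis only, and define its set.
2. State that 80% power applies only with complete follow-up of all 48. Give the expected loss rate and the power at that rate, computed for the analysis actually used. Quote the removal figures (about 76% at 10% loss and 72% at 20%, two-sided) only as the per-protocol case, since they do not describe an analysis that censors.

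Restating the power recovers no information by itself; the first change does that. The second calculation needs the hazard ratio, healing proportions and sidedness behind the 48, so these should be reported with it.

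Cost: SAP wording and a slightly less favourable stated power. No extra patients are needed.

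### The visit schedule places randomisation before Mohs surgery and the Purpose places it after; in the earlier position the >5 mm wound criterion cannot be checked at allocation

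*Combined protocol and SAP*

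**What the plan says.** Four parts of the combined protocol and SAP bear on when patients are allocated.

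- **Purpose.** "After surgery patients will be randomized into two groups". This is the only sentence that expressly times randomisation relative to the operation.
- **Objectives.** Aim 2 states: "We plan to randomize n=48 patients with post-surgical lower extremity wounds". Aim 1 likewise describes randomising patients who have postoperative wounds.
- **Study Design.** After consent, "a screening visit will be performed on their Mohs surgery day and patient eligibility will be determined". The next sentence reads: "Then, patients will be randomized 1:1 to a treatment or control group via computer software". Neither says whether this happens before or after the operation.
- **Patient Visits and Data Collection.** The "initial visit will include preoperative screening for eligibility", along with consent, history and examination. Next: "Once the patient is deemed eligible, enrolled, and signed informed consent, they will be randomized" to laser or sham. The following sentence begins "After the patient undergoes Mohs surgery with the resultant ulcer" and goes on to the laser or sham treatment.

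Study Design and Inclusion Criteria both list, as a condition of entry, "a postoperative wound greater than 5mm in diameter".

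**The concern.** A postoperative diameter cannot be known at a preoperative screening. If the visit section is followed as written, the patient is declared eligible and allocated before one of the inclusion criteria can be assessed. When the defect then measures 5 mm or less, the site has two options: exclude a patient who has already been randomised, or treat one who does not meet the criteria. The plan has no rule for either. The only related text is in Statistical / Data analysis, which answers attrition with a per-protocol analysis and mentions no intention-to-treat analysis, so such patients could drop out of the comparison without a prespecified rule.

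Two things are at stake. The first is some loss of power and balance, even if exclusions are made without knowledge of the arm. The second is selection bias, if a person who knows the arm has a say in whether a borderline wound qualifies. There is also a practical problem: staff working from the Purpose and staff working from the visit section would run different allocation procedures.

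**Working it through.** **1. Order of steps, section by section**

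| Section | Screening | Randomisation relative to surgery |
|---|---|---|
| Purpose | not placed | after (explicit) |
| Aims 1 and 2 | not placed | patients already have wounds; fits "after" but does not fix it |
| Study Design | on the surgery day | follows eligibility; not placed relative to surgery |
| Patient Visits and Data Collection | preoperative | before, by order of sentences |

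The visit section never literally states that randomisation precedes surgery. Preoperative screening, then randomisation, then surgery, then treatment is nevertheless its natural reading, and it is the most detailed account of procedure in the document.

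**2. Can the size criterion be verified at allocation?**

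In the Purpose's order, yes. In the visit section's order, no. No section says who confirms the criterion before treatment. The first scheduled size record, in the Purpose, is at the visit immediately after therapy.

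**3. Possible bias**

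Laser or sham is given after surgery, so treatment cannot alter the wound size used for eligibility. Exclusions made without knowledge of the arm therefore do not bias the comparison. Bias needs someone aware of the arm to influence the decision. The Blinding section names one unblinded member, the treating clinician, and keeps that person out of data collection, which goes to a separate blinded member. One sentence there links blinded collection to later visits, and the pre-treatment size check is given to nobody. The protection is substantial but incomplete.

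**4. Possible loss of power**

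From Statistical / Data analysis: alpha 0.10, beta 0.20, 24 per group, 48 in total. No hazard ratio (HR), healing proportion or sidedness is given, so 48 cannot be reproduced directly. Instead I solve for the HR that 48 implies. With 1:1 allocation and *d* events (healed wounds), Schoenfeld's formula gives

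power = Φ( ln HR × √(d × 0.25) − z ).

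For 80% power with all 48 healing, ln HR = (z + 0.842) / √12:

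- two-sided, z = 1.645: 2.486 / 3.464 = 0.718, HR = 2.05
- one-sided, z = 1.282: 2.123 / 3.464 = 0.613, HR = 1.846

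Suppose 5% or 10% of those randomised are excluded: 48 × 0.05 = 2.4 and 48 × 0.10 = 4.8, or about 2 to 5 patients. Two-sided with all healing:

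- d = 45.6: 0.718 × √11.4 = 2.424; 2.424 − 1.645 = 0.779; power 78.2%
- d = 43.2: 0.718 × √10.8 = 2.359; 2.359 − 1.645 = 0.714; power 76.2%

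| Assumptions | None excluded | 5% excluded | 10% excluded |
|---|---|---|---|
| Two-sided, HR 2.05, all heal | 80.0% (d = 48) | 78.2% (45.6) | 76.2% (43.2) |
| Two-sided, HR 2.05, 85% heal | 74.1% (40.8) | 72.2% (38.76) | 70.2% (36.72) |
| Two-sided, HR 2.05, 75% heal | 69.5% (36) | 67.5% (34.2) | 65.5% (32.4) |
| One-sided, HR 1.846, all heal | 80.0% (48) | 78.5% (45.6) | 76.8% (43.2) |

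The loss is 1.5 to 4.0 percentage points throughout. The lower baselines in rows two and three come from incomplete healing at a fixed HR, not from the order of randomisation.

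**The case against.** The best defence is that there is no real contradiction. The visit section makes randomisation conditional on the patient being deemed eligible. Eligibility includes a postoperative wound above 5 mm, so, applied strictly, nobody can be randomised until the wound exists. On that reading the visit section agrees with the Purpose, and the Aims and Study Design fit too. This does not hold up well, because the visit section itself describes the screening as preoperative and narrates surgery only after allocation. A coordinator following it step by step would randomise first.

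Other objections carry more weight:

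- Study Design does place eligibility before allocation and on a stated day. What is missing is the position relative to the operation and the person responsible.
- The bias route is narrow, since size is fixed before treatment and the sole unblinded member is kept out of data collection. This stands, and bias is not claimed as a likely outcome.
- The exclusion rate is assumed and could be near zero. If 48 means evaluable patients and exclusions are replaced, the power loss disappears. This stands too.
- If the HR is re-solved to give 80% power under incomplete healing (about 2.18 at 85% and 2.29 at 75%), the fall is again 80% to 78.2–76.2%. The healing scenarios therefore do not enlarge the problem.

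**Conclusion.** The concern holds. The Purpose and the visit section give different orders, and in the visit section's order an inclusion criterion cannot be verified when the patient is allocated. This should be fixed because it leaves sites with two allocation procedures, one of which produces either exclusions after randomisation or treatment of ineligible patients.

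The likely numerical effect is modest: 1.5 to 4.0 points of power if 5–10% of the 48 were excluded. That rests on an assumed exclusion rate, HR, healing proportion and sidedness, none of which the document gives. If nobody is excluded there is no such loss, but patients who fail the size criterion are treated. Bias is possible only if someone who knows the arm influences the size decision, and its size cannot be estimated from the document.

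**What to change.** Rewrite Patient Visits and Data Collection in the Purpose's order:

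1. Before surgery: consent, history, examination and all screening that does not depend on the wound.
2. After surgery: a member of the blinded team, not the treating clinician, measures the defect and records whether it meets the existing >5 mm criterion.
3. Only then: randomise.
4. Laser or sham, on the same day.

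State that patients whose wound does not qualify are screen failures and are not randomised. In Study Design, add to the randomisation sentence that it takes place after surgery, so that all sections agree. State also how any patient found ineligible after allocation will be analysed, since the present per-protocol sentence leaves this open.

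The cost is a few sentences of protocol text and one size check between surgery and treatment. The size record scheduled immediately after therapy stays. No extra visits or patients are needed, and no eligibility criterion or treatment changes.

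### Adverse events are coded only yes/no, with no severity grade, no pain item, overlapping scar items and no stated code for unlisted events, although Aim 1 is about tolerability

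*Combined protocol and SAP*

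**What the plan says.** The recording rule is under Patient Visits and Data Collection: "Adverse events will be recorded as presence of absence of specific outcomes". The prompted items follow: "Outcomes that patients will be directly questioned about include: crusting (scaly or thickened scar), swelling, burning sensation, xerosis at treatment site, pruritus at treatment site", then "infection, bleeding, hypertrophic or keloid scarring, burns, or color changes at treatment site". That makes ten items. The section describes no severity grade, no pain item (burning sensation is the nearest) and no line for other events.

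The same section gives two sources: "Adverse events will be recorded by eliciting an oral history and review of the patient's diary". The items are collected at every visit and adjudicated by a blinded team member.

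Two other sections bear on unlisted events. Study Design says "Patients will be given a diary to record observations about their postoperative wound and to note any adverse events". Blinding says the unblinded treating clinician takes no part in data collection but "will be responsible for reporting any adverse events per IRB protocols at our institution".

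Aim 1, under Objectives, sets out to establish safety and tolerability through "assessment of safety endpoints, including the incidence of wound infection and tolerability using a patient diary", together with a quality-of-life questionnaire. Statistical / Data analysis names models for infection and quality of life. It names no summary or analysis for the other nine items.

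**The concern.** Tolerability is a matter of degree, and a yes/no code scores faint swelling and marked swelling alike. Several prompted items (crusting, swelling, color change, itching) may well occur in an untreated open surgical wound. The plan's own definition of healing requires that no scab or eschar remain, so it expects some crusting before closure. For such signs the useful question is how bad they are, not whether they occur. The trial could report similar rates in the two arms while reactions in the laser arm were worse, and the result would be read as good tolerability.

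Two smaller gaps add to this. A thickened scar meets the gloss on crusting and also the hypertrophic or keloid item, so two assessors could code one sign differently. And an event off the list, pain included, may be written in the diary or told to the assessor, but the plan does not say how it then enters the trial data.

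**Working it through.** **What the documents supply.** 24 patients per group and alpha 0.10 (Statistical / Data analysis; sidedness not stated, taken here as two-sided), and 1:1 allocation (Study Design). The sample size of 48 is for time to epithelialization and does not bear on how events are coded, so there is no plan figure to reproduce. No adverse-event rate is given. Every rate and odds ratio below is an assumption.

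**Step 1: how high must the background rate be before yes/no fails?** Take the extreme case in which all 24 laser patients show the sign. Fisher's exact test gives p = 0.109 if 20 of 24 sham patients show it and p = 0.050 if 19 of 24 do. A difference is therefore declared only if at most 19 sham patients show the sign, and power is P(X ≤ 19) with X ~ Binomial(24, sham rate):

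- sham rate 95%: 0.6%
- sham rate 90%: 8.5%
- sham rate 70%: 89%

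The ceiling is severe at about 90% and above, and absent at 70% against 100%.

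**Step 2: yes/no against a grade.** Assume four levels (none, mild, moderate, severe) and let the laser multiply the odds of being at or above each level by OR. The assumed sham distributions are (.05, .55, .30, .10), (.10, .50, .30, .10), (.20, .50, .20, .10) and (.50, .30, .15, .05).

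For any occurrence, laser rate = OR·o/(1 + OR·o), where o = p/(1 − p) and p is the sham rate. At OR 3:

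- p = 95%: o = 19, 57/58 = 98.3%
- p = 90%: o = 9, 27/28 = 96.4%
- p = 80%: o = 4, 12/13 = 92.3%
- p = 50%: o = 1, 3/4 = 75%

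The other levels move in the same way. In the 90% row, moderate or worse goes from 40% to 2/(1 + 2) = 66.7%, and severe from 10% to (1/3)/(4/3) = 25%.

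Yes/no power is exact: the sum of binomial probabilities over all tables with Fisher p ≤ 0.10. Power for the grade is from the Wilcoxon rank-sum test in 6,000 simulated trials per row (simulation error about 0.6 points).

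| Sham rate | Yes/no, OR 3 | Grade, OR 3 | Yes/no, OR 2 | Grade, OR 2 |
|---|---|---|---|---|
| 95% | 0.4% | 64% | 0.4% | 35% |
| 90% | 4.6% | 65% | 3.5% | 36% |
| 80% | 21% | 65% | 13% | 35% |
| 50% | 45% | 65% | 23% | 36% |

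The grade has more power in every row at both odds ratios, so the case for grading does not depend on a ceiling. The gain is largest where the sign is nearly universal and moderate at 50%.

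**Step 3: unlisted events.** Set the sections side by side. The recording rule is presence or absence of specific outcomes. The prompt list is introduced by a word that does not make it exhaustive. Oral history and an open diary can bring other events to light. The treating clinician's duty runs to the IRB, and that clinician is kept out of data collection. So unlisted events can surface and be reported, but no sentence carries them into a coded field of the trial data.

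**The case against.** A reader might infer that the list is closed and that unlisted events go unrecorded. The documents do not support that. The list is only said to include the ten items, the diary is for any adverse events, oral history is taken, and the clinician reports any adverse events to the IRB. What is missing is a coding rule. The case-report form itself is not part of the documents.

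A reader might also infer that yes/no data cannot separate the arms. That depends on background rates of about 90% or more, which the documents do not give. It does not fit infection, burns or keloid scarring, which are not features of every open wound and for which presence or absence is a reasonable code. The items are also recorded at each visit, so yes/no data could show a difference in how long a sign persists. A single any-versus-none comparison leaves that out.

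The power figures are open to challenge as well: proportional odds with a ratio of 3 is a choice, at 2 the grade reaches only about 35%, and the plan proposes neither test for these items. Tolerability also draws on the diary and quality of life, and burning sensation covers part of pain.

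All of this limits the point but does not remove it. Persistence is not severity, the plan names no analysis by visit for these items, and none of the other sources gives a graded comparison of local reactions by arm.

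**Conclusion.** The point holds in this limited form. The stated rule codes adverse events yes/no, without severity or pain, with two items that overlap on thickened scar, and without a stated code for unlisted events. For signs common in both arms this discards information that Aim 1 needs, and similar rates should not be read as similar tolerability.

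The size is conditional. Under the assumed distributions with 24 per arm and two-sided 10%, the loss at an odds ratio of 3 runs from 65% against 45% power (sham rate 50%) to 64% against 0.4% (sham rate 95%). At an odds ratio of 2 it runs from 36% against 23% to 35% against 0.4%. Grading makes better use of 48 patients, but does not make the trial well powered for modest differences in tolerability. This is a cheap improvement to data capture. It does not undermine the infection comparison or the healing endpoint.

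**What to change.** At each visit have the blinded assessor record none, mild, moderate or severe for each listed item, with a short written anchor for each grade. Add pain and an other (specify) line, so that events from the diary or oral history have a place in the data. Define crusting as scab or scale, and leave thickened scar to the hypertrophic or keloid item. State in the analysis section that worst grade per patient will be summarised by arm for every item.

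The cost is one revised case-report page and a sentence in the analysis section. No new visit or assessor is needed. The downsides are slightly longer visits and some subjectivity in grading, which the blinded assessment already planned helps to keep even between the arms.
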